6.4.1. Unblinding

In the event of a medical emergency where knowledge of subject's study drug assignment is necessary per the medical judgment of the Investigator, the Investigator may break the blind using the randomization system. If possible, the Sponsor's Medical Monitor should be notified before the Investigator breaks the blind to discuss the case. If not possible, the Sponsor's Medical Monitor should be notified as soon as possible after breaking a treatment code. The unblinding must be clearly justified and explained by a comment in the source documentation, along with the date on which the code was broken and the identity of the person authorizing the unblinding.

Only the Investigator or delegate should be unblinded to the subject's code. Site personnel and Sponsor personnel directly associated with the conduct of the study should not be unblinded.

Additionally, the Sponsor's delegate may unblind the treatment for an individual subject's serious adverse event (SAE) if needed to fulfill expedited regulatory reporting requirements, or the Safety Review Committee (SRC) may have access to the treatment code, if needed.

6.5. Dose Modification

This is a single-dose study. No dose modifications by the Investigator are permitted.

6.6. Encapsulation, Packaging and Labeling

Study drug must be stored under the conditions specified on the label and remain in the original container until dispensed.

6.7. Handling/Storage/Accountability

The process for each site to abide by the security controls detailed by the Drug Enforcement Agency (DEA) surrounding Schedule I drugs is described in the DEA Site Security Agreement. The Investigator is responsible for ensuring compliance at the site with all procedures outlined in the DEA Site Security Agreement.

Additionally, details of drug handling, storage and accountability will be included in the Pharmacy Manual, which will provide information on tamper-proof dispensing, the maximum time period allowed between removal of drug from secured storage until dosing, tracking, control and return via reverse distributor, and prevention of unauthorized access.

Study drug should be stored in a secure (recommended double-locked and bolted to the floor/wall), limited-access location. Sites will ensure proper perimeter and internal physical security is in place to prevent any diversion or theft of study drugs.

At any time from the site's receipt of study drug until the final collection of study data, drug accountability discrepancies will be monitored as follows:

- The site will conduct drug accountability by site delegated team member and readily retrievable.
- Any time the site identifies a discrepancy or possible diversion, the Sponsor must be notified promptly. For any discrepancy that triggers a drug accountability check, the Investigator or designee must resolve it promptly and will complete the eCRF page and ensure state, federal and ethics committee reporting is accomplished. The triggering drug accountability discrepancies are as follows:
 - Compliance issues where 1 or more subjects' masked supplies are used more than the expected use, according to the drug accountability calculations
 - Missing masked supply capsule(s)
 - Evidence of tampering

The Investigator is required to indicate the level of certainty of the classification and enter this into the subject's eCRF for the trial. The Sponsor or their designee will review and confirm classified triggered cases and detail conclusions and recommendations (see Section 9.9 on Special Situations).

The Investigator is responsible for ensuring accurate records are kept of the study drug received from the Sponsor or designee, the amount dispensed to the subjects and the amount remaining at the conclusion of the trial. Receipt and dispensing of study medication must be recorded by an authorized person at the study site.

Study drug may not be used for any purpose other than that stated in the protocol. DEA storage and dispensing procedures must be strictly followed to prevent the illegal distribution and/or abuse of study drug by subjects or site staff (i.e., diversion). In addition, study subjects must be administered study drug under the supervision of the study drug dispenser and dosing session monitors.

Each site will have a practitioner who is a Schedule I license holder.

6.8. Study Drug Compliance

All subjects will be dosed at the site and will receive study drug directly from the Investigator or designee under medical supervision; the study drug administration will be witnessed by the Investigator and/or Dosing Session Monitor(s). The date and time of study drug administration at the site will be recorded in the source documents and the eCRF.

The randomized study drug and study subject identification will be confirmed at the time of administration by a member of the study site staff other than the person administering the study drug. The study site personnel administering the dose will examine the subject's mouth and hands to ensure that the study drug was ingested.

6.9. Study Drug Overdose

Refer to Section 9.5 for the definition of overdose and overdose management and refer to Section 9.9 for information on overdose reporting.

6.10. Concomitant Therapies

All medications, therapies and supplements taken by the subject during the course of the study will be recorded. Upon entry into the study, subjects will be instructed to report the possible need for any prescription or nonprescription medications, therapies and supplements immediately (and before use) to the Investigator.

Subjects should remain on a stable regimen of all allowable medications from Baseline (Visit 2) until End of Study and will be excluded from the study if they plan to initiate, stop, or alter concomitant medication use during this time.

Medications and supplements to treat anxiety, depression or other mood disorders will be tapered prior to Baseline (Visit 2) (see Section 8.1.6 for information on medication tapering). As subject safety is paramount, any treatments considered necessary for the subject's welfare may be given during the study at the discretion of the Investigator. If the permissibility of the drug treatment is questionable, the Sponsor's Medical Monitor must be consulted.

6.10.1. Prohibited Medications, Supplements and Therapeutics

The use of medications, supplements and other therapeutics (over-the-counter or prescribed) for treating anxiety, depression or mood disorders are prohibited from Baseline (Visit 2) until End of Study (except if needed during Day 1/Dosing Session [Visit 3B], as noted in Table 5. Additionally, the use of other substances, supplements, etc. that may confound the results of the study are prohibited from Baseline (Visit 2) until End of Study (e.g., cannabis, cannabidiol [CBD], ginkgo biloba).

Subjects must also avoid starting, stopping or altering non-medicinal therapies from the time of providing informed consent until End of Study, as described in Section 5.2.3.

Any prohibited substance(s) being taken at the time of Screening (Visit 1) should be tapered prior to at Baseline (Visit 2), if safe for the subject, in the opinion of the Investigator; tapering

will be done with oversight from the study site designated physician and in accordance with information provided in Section 8.1.6.

Table 5 provides a listing of specific restrictions for concomitant therapy use during the course of this study, with any necessary washout periods or allowable conditions described. This table provides examples; however, it is not a comprehensive list of all restricted medications, supplements and other therapeutics. Consult the Sponsor's Medical Monitor or designee if there is any uncertainty regarding a subject's use of a particular drug, drug class, supplement or other therapeutic.

Subjects on prohibited medications, supplements or other therapeutics at the time of Screening (Visit 1) may taper off that substance (see Section 8.1.6) and participate in the study if the required washout conditions have been met. For prescribed medications to treat anxiety, depression or other mood disorders, the medication taper will be overseen by the study site designated physician based on acceptable local practice standards.

The final decision to continue or discontinue any medications/supplements/therapeutics that the subject is taking rests with the subject, the study site designated physician and/or the subject's primary care provider. However, the decision to have the subject receive study drug requires the mutual agreement of the Investigator, the Sponsor and the subject.

[figure not shown]
Clinical Study Protocol: MMED008

Table 5: Listing of Prohibited Medications, Supplements and Other Therapies

Drug Class or Drug Name	Washout Conditions/ Prohibition Period ^a	Allowable Conditions
Benzodiazepines	Last dose must have been taken at least 5 half-lives prior to Day 1/Randomization (Visit 3A)	To treat anxiety during Day 1/Dosing Session (Visit 3B), at Investigator's discretion ^b
Lithium	Last dose must have been taken at least 7 days prior to Day 1/Randomization (Visit 3A)	None
Monoamine oxidase inhibitors (MAOIs) ^c	Last dose must have been taken at least 3 weeks prior to Day 1/Randomization (Visit 3A)	None
Antipsychotics – traditional		
Antipsychotics – atypical	Last dose must have been taken at least 5 half-lives prior to Day 1/Randomization (Visit 3A)	None
Atypical agents (e.g., bupropion, mirtazapine)		
Barbiturates Selective serotonin reuptake inhibitors (SSRIs). NOTE: fluoxetine washout is 35 days		
Serotonin-norepinephrine reuptake inhibitors (SNRIs)		
Serotonin–norepinephrine–dopamine reuptake inhibitors (SNDRIs)		
Serotonin modulators (e.g., vortioxetine, trazodone)		
Tricyclic antidepressants (TCAs)		
Stimulant (e.g., methylphenidate hydrochloride)		
Cannabis ^d	Prohibited from Baseline (Visit 2) through End of Study	None
Other medications, supplements, or therapeutics that affect serotonergic function (e.g., efavirenz, Kava, ginkgo biloba, St. John's Wort, 5-hydroxytryptophan [5-HTP], ayahuasca, dimethyltryptamine [DMT])	Last dose must have been taken at least 5 half-lives prior to Day 1/Randomization (Visit 3A)	None

Note: This table is not a comprehensive list of all restricted medications or supplements. Consult the Sponsor's Medical Monitor or designee with any questions about specific medications, supplements or therapeutics.

- ^a Subjects on prohibited medications, supplements or other therapeutics at the time of Screening may taper off that substance(s) prior to Baseline (Visit 2) (see Section 8.1.6) and will be eligible to participate in the study if the required washout conditions have been met. Investigator must consider the half-life of active metabolites.
- Benzodiazepines should only be offered and administered if non-pharmacological interventions (e.g., reassurance, verbal communication) do not adequately address severe anxiety during the Dosing Session.
- ^c Although the half-life of MAOIs is typically 1.5-4 hours (eliminated quickly), the irreversible inhibition of monoamine oxidase may persist for 2-3 weeks due to the requirement for *de novo* synthesis of new enzyme, which is a relatively slow process. Therefore, washout for any MAOI should be conservatively 3 weeks.

6.10.3. Permitted Medications, Supplements and Therapeutics

Consult the Sponsor's Medical Monitor or designee if there is any uncertainty regarding a subject's use of a particular drug, drug class, supplement or other therapeutic.

6.11. Treatment after the End of the Study

Subjects will not receive any additional treatment with study drug from the Sponsor after completing the study. The Investigator is responsible for ensuring that consideration has been given to the post-study care of the subject's mental health and physical health. Sites must refer subjects for ongoing psychiatric care at the end of the study.

Clinical Study Protocol: MMED008

7. WITHDRAWAL/DISCONTINUATION

7.1. Discontinuation of Study Drug

This is a single-dose study, and thus, discontinuation of study drug is not applicable.

7.2. Early Withdrawal from the Study

Subjects may withdraw consent at any time for any reason or be withdrawn from the study at the discretion of the Investigator should any untoward effect occur. A subject may be withdrawn by the Investigator or the Sponsor if enrollment into the study is inappropriate, the protocol is violated or for administrative and/or other safety reasons. The subject may be discontinued from further study participation after discussion between the Investigator and the Sponsor's Medical Monitor (or designee) if the subject requires therapy with any excluded medication (see Section 6.10.1). Every effort should be made to establish and document the possible reason(s) for withdrawal.

A subject must be discontinued from the study for any of the following reasons:

- The subject withdraws consent.
- The subject has a medical condition or personal circumstance that precludes the subject from attending future study visits, does not allow the subject to adhere to the requirements of the protocol or, in the opinion of the Investigator and/or Sponsor, places the subject at unnecessary risk through continued participation in the trial.

When a subject discontinues/withdraws prior to study completion (i.e., prior to Week 12 [Visit 9]), he/she should return to the clinic to complete an Early Withdrawal visit (same assessments/procedures as Week 12 [Visit 9]) or if the subject is at the site at the time of early withdrawal, all applicable activities scheduled for the final study visit should be performed at the time of discontinuation. The Sponsor's Medical Monitor or designee should be notified within 24 hours if the withdrawal is due to an SAE and within 7 days if the withdrawal is due to another reason

Any AEs that are present at the time of discontinuation/withdrawal should be followed in accordance with the safety requirements outlined in Section 9.

Once a subject is discontinued, the subject shall not be allowed to enroll again.

As this is a single-dose study, if a subject becomes pregnant after Day 1/Dosing Session (Visit 3B), they are not required to withdraw from the study. The subject will be monitored for the pregnancy outcome, and reporting will occur as described in Section 9.10.

Sites must refer subjects withdrawn early for ongoing psychiatric care.

Lost to Follow Up

Should a subject fail to attend a required study visit, the site should attempt to contact the subject and re-schedule the missed visit as soon as possible. The site should also counsel the

Clinical Study Protocol: MMED008

subject on the importance of maintaining the assigned visit schedule and ascertain whether or not the subject wishes to and/or should continue in the study based on previous non-compliance. In cases where the subject does not return for the rescheduled visit or cannot be reached to reschedule the missed visit, the site should make every effort to regain contact with the subject (3 documented telephone calls and, if necessary, a certified letter to the subject's last known mailing address) so that they can appropriately be withdrawn from the study with a primary reason of "Lost to Follow-up". Efforts to establish the possible reason for discontinuation should be documented.

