9.4.1. Period for Reporting Adverse Events

AE collection will occur from the time informed consent is given until completion of the study and will be recorded at each visit.

Any event occurring between signing of the ICF and dosing with study drug at Day 1/Dosing Session (Visit 3B) will be recorded as medical history in the eCRF and in the subject's clinical record for any subject who continues to meet eligibility criteria and proceeds to dosing with study drug.

Adverse events collected from the time study drug is administered through End of Study (Week 12 [Visit 9] or Early Withdrawal) will be recorded on the AE page of the eCRF. SAEs and/or AESIs suggestive of abuse potential will be collected from the signing of the informed consent form until the Week 12 (or Early Discontinuation) visit. SAEs and/or AESIs suggestive of abuse potential reported to the Investigator after the safety reporting period should be reported to the Sponsor if the Investigator assesses the event as related to the study drug treatment.

Reporting instructions for SAEs and/or AESIs suggestive of abuse potential are provided in Section 9.4.2.

9.4.2. Reporting Serious Adverse Events and Adverse Events of Special Interest Suggestive of Abuse Potential

All SAE and/or AESIs suggestive of abuse potential must be reported within 24 hours of the study site personnel's knowledge of the event, regardless of the Investigator's assessment of the relationship of the event to study drug. The events will be entered into the EDC and the narrative section provided in the drug safety database.

The minimum criteria for SAE and/ or AESI suggestive of abuse potential reporting are as follows: the event or outcome meets the definition of an SAE and/ or AESI suggestive of abuse potential (see Section 9.2 and Section 9.3); the event happens to an identifiable study subject; and the event is reported by an identifiable and qualified reporter (usually the Investigator or other qualified study site personnel).

A follow-up report to an SAE and/ or AESI suggestive of abuse potential should be prepared if any relevant change in the condition of the study subject occurs after the initial report. The follow-up report should be documented as an update to the initial report.

If the subject died, the report should include the cause of death as the event term (with death as the outcome) and whether or not the event leading to death was related to study drug, as well as the autopsy findings if available.

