## 4.2 Analysis Sets

The following populations will be defined for the purpose of analysis:

- Randomized Set (RAN) all subjects who received a randomization number, regardless of receiving study drug. Subjects will be analyzed according to the treatment assigned.
- Safety Set (SAF) all subjects who received the double-blind study drug. Subjects will be analyzed according to the actual treatment received.
- Full Analysis Set (FAS) all randomized subjects with a valid baseline HAM-A assessment and at least one valid post-baseline HAM-A assessment. Subjects will be analyzed according to the treatment assigned.
- Per Protocol Set (PPS) All subjects in the full analysis set who had no major protocol deviations deemed as impacting the primary endpoint. Subjects will be analyzed according to the actual treatment received.

An impact assessment will be performed prior to the unblinding of the study. The impact assessment will determine whether a major protocol deviation impacts the primary endpoint thereby leading to the removal of the respective subject(s) from the PPS.

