## 6.1.1 Handling of Missing Data and Potentially Biased Values

Missing data for the primary endpoint will be imputed using a multiple imputation approach assuming that the missingness mechanism can be retrieved from observed data. The imputation model will include the treatment group and the longitudinal sequence of HAM-A Total Score. Imputations will be performed 20 times using SAS PROC MI with the fully conditional specification (FCS) method.

For intercurrent events (IEs) the following methods will be used:

- The data recorded after the IE will be set to missing and imputed under a Missing Not at Random (MNAR) assumption by borrowing information from the placebo arm subjects (reference-based imputation) for the following:
  - Concomitant/prohibited medications that meet the threshold for impact = "Yes" during the impact assessment will be considered as the IE. Any observations after such an IE will be set to missing and will be imputed using the MNAR assumption.
- Available data will be used; missing data will be imputed under a Missing at Random (MAR) assumption, borrowing information from subjects in the same treatment arm for the following:
  - For IEs leading to study discontinuation due to other reasons
  - IEs related to the COVID-19 pandemic.

For missing data not due to IEs the imputation will be performed based on MAR assumption.

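### Protocol 7.2 allows dosed subjects to be withdrawn for inappropriate enrolment, protocol violation or administrative reasons, which stops no treatment in a single-dose trial but cuts short outcome and safety follow-up

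*Protocol*

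**What the plan says.** Protocol 7.2 gives a discretionary rule: "A subject may be withdrawn by the Investigator or the Sponsor if enrollment into the study is inappropriate, the protocol is violated". The same sentence also permits withdrawal on administrative or safety grounds. Nothing confines the rule to the period before dosing. A separate list makes withdrawal mandatory for loss of consent, and for a condition or circumstance that prevents attendance, prevents adherence to protocol requirements or creates unnecessary risk. The lost-to-follow-up text in the same section asks sites to consider whether a subject should stay in, given earlier non-compliance.

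Protocol 7.1 says: "This is a single-dose study, and thus, discontinuation of study drug is not applicable". For a pregnancy after dosing, 7.2 gives the single-dose design as the reason that "they are not required to withdraw from the study".

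A withdrawn subject should have an Early Withdrawal visit with the Week 12 assessments, and AEs present at that time are followed. Under Protocol 9.4.1, SAEs and AESIs "will be collected from the signing of the informed consent form until the Week 12 (or Early Discontinuation) visit"; later ones are reported if judged related.

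On the analysis side (Protocol Table 8, SAP 4.2), the FAS takes randomized subjects with a valid baseline and at least one valid post-baseline HAM-A, analysed as assigned. The PPS takes FAS subjects "who had no major protocol deviations deemed as impacting the primary endpoint". SAP 6.1.1 uses available data and imputes missing values under MAR from the same arm in the category "For IEs leading to study discontinuation due to other reasons". Medication use judged to have an impact is treated differently: later scores are set to missing and imputed from placebo under MNAR.

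**The concern.** For a dosed subject, a violation, a late-found eligibility failure or an administrative reason gives nothing to discontinue except observation. The analysis plan already has a place for such subjects: they stay in the FAS as assigned, and the PPS removes those whose deviation affects the endpoint. That comparison is informative only if deviators go on being measured.

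Such events can surface after dosing. Cannabis and other substances are prohibited to End of Study (Protocol 6.10.1), drug screens are scheduled at every visit from Week 1 to Week 12 (Protocol Table 2), and history first learned after Screening is still recorded (Protocol 8.1.5).

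Three things are at stake:

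- Week 4 and Week 8 HAM-A values become modelled instead of observed for a group selected by judgement after dosing. The protocol itself foresees functional unblinding (2.4, 8.4.5), so the decision could depend on perceived treatment or on how the subject is doing. MAR is least secure for such withdrawals.
- The FAS-versus-PPS comparison lacks these subjects' scores after withdrawal.
- Routine SAE/AESI and C-SSRS collection stops before Week 12.

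**Working it through.** **1. The plan's own figure.** Protocol 10.2.2.2 and SAP 9 assume 36 per arm in five arms, a maximum effect of 0.6 SD, one-sided 0.05 and six candidate curves. The statistic for each optimal contrast c has non-centrality c'μ / √(Σcᵢ²/n), with 180 − 5 = 175 df. Simulation of the six-variate t (400,000 draws) gives a critical value of 2.04.

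| Candidate | Stated power (%) | Recomputed (%) |
|---|---|---|
| Sigmoid Emax 10, 1 | 84.5 | 84.7 |
| Sigmoid Emax 100, 5 | 90.7 | 90.8 |
| Sigmoid Emax 100, 10 | 91.0 | 91.1 |
| Sigmoid Emax 150, 10 | 89.9 | 90.0 |
| Emax 100 | 83.2 | 83.4 |
| Linear | 85.0 | 85.1 |

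The stated mean is 524.3/6 = 87.4%. The recomputed mean is 87.5%, and 87.3% in a second run. The stated power is right on its inputs. No dropout allowance is stated.

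**2. What is lost, by timing.** SAP 4.3 assigns HAM-A values from all scheduled and unscheduled visits by study day: Week 4 is Days 22-43 and Week 8 is Days 44-71.

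- Last HAM-A before Day 22: Week 4 and Week 8 are unobserved.
- Last HAM-A on Days 22-43: Week 4 can be observed (the Early Withdrawal value can serve), but Week 8 is not.
- No post-baseline HAM-A at all (the first is scheduled at Week 1, and none is obtained at the Early Withdrawal visit): the subject is outside the FAS and is not imputed.
- Safety: a subject withdrawn at Week 1 forgoes 12 − 1 = 11 of the 12 planned weeks of follow-up.

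**3. Bias in an arm mean.** The documents give no withdrawal rate and no departure from MAR, so both inputs are assumptions. Let f be the fraction of an arm withdrawn this way before Week 4, and δ the gap between their true mean outcome and the MAR prediction. Then shift = f × δ.

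| f | δ (SD) | Shift (SD) | Share of 0.6 SD | Share of SE of a two-arm difference |
|---|---|---|---|---|
| 0.03 | 0.3 | 0.009 | 1.5% | 4% |
| 0.05 | 0.5 | 0.025 | 4.2% | 11% |
| 0.10 | 0.8 | 0.080 | 13.3% | 34% |

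The SE is √(2/36) = 0.236 SD. In subjects, 3% of 36 is about 1 and 10% is 3.6.

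The drug-placebo contrast moves by f_drug × δ_drug − f_placebo × δ_placebo, which is zero if the arms are affected equally. The last two columns therefore show the case in which only one arm is affected.

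**4. Power.** Assume equal losses across arms with nothing recovered by imputation. Mean power is then 86.6% with one lost per arm (n = 35), 85.5% with two (n = 34) and 84.0% at 10% loss. These overstate the loss, because earlier and Early Withdrawal scores feed the imputation model.

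**The case against.** The strongest reply is that little is lost. A reader might infer from 7.2 that withdrawal deletes data or removes the subject from analysis. The documents do not support that. Nothing removes collected data, a full exit visit is specified, AEs present at withdrawal are followed, subjects are referred for psychiatric care, and every dosed subject stays in the Safety Set. This stands.

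Nor does every such subject lack a Week 4 score, since an Early Withdrawal HAM-A on Days 22-43 can serve. Scores before withdrawal stay in the FAS and inform the imputation. Only later scores are missing.

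MAR is also not universal here. Medication use judged to have an impact goes to placebo-based MNAR imputation, so continued visits would give the primary analysis no observed Week 4 score after that event. This stands too, and limits what the fix can gain.

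The PPS analysis is the only one labelled as sensitivity, but not the only extra look. SAP 6.1.2 repeats the modelling with the single best model, and SAP 6.3.1 gives an ANCOVA on FAS and PPS, for which SAP 4.5 plans no imputation. None of these tests a different missing-data assumption for these withdrawals.

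Finally, the clause is permissive, eligibility is checked at three visits without waivers (Protocol 8.1.4), and HAM-A is scored by remote central raters with no site staff in the room (8.4.3). These points make such withdrawals less likely and protect the rating. They do not protect the decision to withdraw, which rests with the site or the sponsor.

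**Conclusion.** The point holds as a cheap improvement. For a dosed subject the three grounds stop no treatment. They create an avoidable, judgement-driven loss of Week 4 or Week 8 HAM-A and of routine safety follow-up. This sits badly with an as-assigned FAS, with a PPS that already handles deviations, and with the section's own reasoning on pregnancy.

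The size is unknown and probably small. The range of 0.009-0.08 SD in one arm mean rests wholly on the assumed 3-10% and 0.3-0.8 SD. The direction cannot be stated, and the upper end needs both extremes together. An equal shift across arms cancels.

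A reader might also infer a sample-size error. There is none: the stated power reproduces. The >87% target does have almost no slack, but the main issue is selective missingness, not power.

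**What to change.** In Protocol 7.2, limit inappropriate enrolment, protocol violation and administrative reasons to subjects not yet dosed. After dosing, record such events as deviations and continue the scheduled assessments to Week 12, unless consent is withdrawn, the subject cannot attend, or continued participation poses a risk. Leave all safety grounds unchanged.

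Two other parts of 7.2 must be reconciled with this: the mandatory ground on inability to meet protocol requirements, and the lost-to-follow-up text on previous non-compliance.

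In the SAP, state that observed scores of these subjects are used in the FAS, except where the existing medication-impact rule sets them to missing, and that deviations are handled through the PPS.

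The cost is a protocol amendment, which needs IRB/IEC approval before use (Protocol 11.7), and a few more deviators on a visit schedule that already exists. SAP 8 says enrolment has ended, so the gain in this trial is limited to subjects still in follow-up when the change takes effect.
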